6.13 Safety analysis

All subjects who receive at least dose one of study medication will be included in the analysis of safety.

Safety measures will be summarized for the following subject cohorts for the open label phase:

- All treated subjects;
- Treated subjects without urinary evidence of illicit drug use; and
- Treated subjects with urinary evidence of illicit drug use (may be further subdivided by type of illicit drug used).

Safety measures will only be summarized for all treated subjects for the double blind phase.

Extent of exposure

Extent of exposure will be described by whether the subject took the trial medication and the number of days exposure to double-blind study medication (last date of double-blind medication minus first date of double-blind medication + 1). Average daily dose of double-blind study medication will also be calculated. Exposure to open-label medication will also be calculated as last date of open-label medication - first date of open-label medication + 1. No allowance will be made for breaks in therapy in the exposure calculations. Average daily dose of open-label study medication will also be calculated. If the date of last dosing is completely missing for the trial medication then the date of last dosing will be taken for analysis purposes

Effective: 14-Feb-13

Page 18 of 26

as the date the medication was last dispensed. If only the month of the last dose is recorded, the first day of the month will be assumed as the last dosing date.

Adverse Events During the Double-Blind Phase of the Study

All AEs will be listed and tabulated by severity, relationship to study medication, primary system organ class and preferred term according to MedDRA Version 16.0. In counting the number of events reported, a continuous event, i.e., an event reported more than once and which did not cease, will be counted only once with the worst recorded severity; non-continuous AEs reported several times by the same subject will be counted as multiple events. Events present immediately prior to the first dose of study medication that do not worsen in severity, will not be regarded as treatment emergent. Events with start dates more than 30 days after the administration of the last dose of study medication will not be considered treatment emergent and will be listed separately. In deriving the tabulation relating to preferred term reporting, the severity of a recurrent AE will be taken to be the most severe and the relationship to study medication as the highest probable.

The following will be summarized and presented for the overall population and by treatment group:

- The number and percentage of subjects experiencing at least 1 treatment emergent TEAE by MedDRA preferred term and SOC. A chi-squared test will be used to test for a difference in the percentage of subjects experiencing at least 1 TEAE between each of the 2 Lofexidine doses and placebo.
- The number and percentage of subjects experiencing an opioid withdrawal related TEAE by MedDRA preferred term and SOC.
- The number and percentage of subjects experiencing TEAEs by severity of event
- The number and percentage of subjects experiencing TEAEs by relationship to IP
- The number and percentage of subjects experiencing treatment-related adverse events (i.e. Possibly Related, Probably Related, Definitely Related)
- The number and percentage of subjects experiencing at least 1 treatment emergent SAE by MedDRA preferred term and SOC
- The number and percentage of subjects experiencing SAEs by severity of the event
- The number and percentage of subjects experiencing SAEs by relatedness to IP

Adverse events whilst receiving Lofexidine therapy during the open-label phase

All AEs reported whilst receiving Lofexidine therapy will be listed and tabulated by treatment, severity, relationship to study medication, primary system organ class and preferred term according to Version 16.0 of MedDRA. In counting the number of events reported, a continuous event, i.e., an event reported more than once and which did not cease, will be counted only once with the worst recorded severity; non-continuous AEs reported several times

Effective: 14-Feb-13

Page 19 of 26

by the same subject will be counted as multiple events. Events present immediately prior to the first dose of Lofexidine during the open-label phase that do not worsen in severity, will not be regarded as treatment emergent. Events with start dates more than 30 days after the administration of the last dose of Lofexidine will not be considered treatment emergent and will be listed separately. In deriving the tabulation relating to preferred term reporting, the severity of a recurrent AE will be taken to be the most severe and the relationship to study medication as the most probable.

For data analysis purposes, all TEAEs for which data are missing regarding assessments of relatedness and/or severity will be defaulted to be assessed as being related and at the highest severity grade, respectively. Missing or incomplete TEAE start dates will be imputed to correspond with the date of dosing.

Narratives of deaths, serious and other significant adverse events will be provided in the relevant section of the CSR.

A complete subject listing of all adverse events will be provided in Appendix 16.2 to the study report. This listing will include treatment, AE verbatim, MedDRA primary system organ class and preferred term, the time of onset and cessation of event relative to first dosing of study medication, duration of AE (for ongoing AEs use the date of investigator signature as the cessation date for calculation purposes), whether serious, severity, relationship to study medication, action taken and outcome.

Treatment emergent and non-treatment emergent events will be listed separately.

Clinical Laboratory Evaluations

Descriptive statistics will be calculated for the last double-blind and last open-phase postbaseline assessment as well as changes from baseline for each hematology, coagulation and chemistry variable. Each measurement will be classed as below, within, or above normal range, based on ranges supplied by the laboratory used. Shift tables in relation to the normal range from screening to each follow-up visit will be presented.

Descriptive statistics for urinalysis will be calculated for the last double-blind and last openphase post-baseline assessment as well as changes from baseline.

Details of microscopic urinalysis will be provided in Appendix 16.2 of the report.

Vital Signs During the Double-Blind Phase

Vital signs (blood pressure and pulse [sitting or recumbent and standing], respiration, and temperature) will be measured at screening, baseline and before each dose and 3.5 hours after each dose (with the exception of the dose taken at 11 PM, where the measurement at 3.5 hours post-dose will not be done) during the double-blind phase. Summary statistics for observed and changes from baseline will be tabulated at each follow-up for each vital sign parameter and at post-baseline double-blind endpoint for each variable.

Effective: 14-Feb-13

Page 20 of 26

In addition the number and proportion of subjects having:

- Systolic blood pressure \geq 180mmHg and an increase of \geq 20mmHg from baseline
- Systolic blood pressure ≤ 90mmHg and a decrease ≥ 20mmHg from baseline
- Diastolic blood pressure ≥ 105mmHg and an increase ≥ 15mmHg from baseline
- Diastolic blood pressure ≤ 50mmHg and a decrease ≥ 15mmHg from baseline

will be summarized at each follow-up visits.

Vital Signs During the Open-Label Phase

Vital signs (blood pressure and pulse [sitting or recumbent and standing]) will be assessed for one dose every day at pre-dose and 3.5 hours post-dose on Days 8-13, with vital signs measured once pre-dose on Day 14. Summary statistics for observed and changes from baseline will be tabulated at each follow-up and at post-baseline open-phase endpoint for each variable.

Mean profiles by treatment will be presented for sitting and standing blood pressure and heart rate.

ECG

ECG data collected during the double-blind and open-label phase will be analyzed separately in a stand-alone report.

In addition, PI overall interpretation of the ECG (Normal, Abnormal NCS, and Abnormal CS) will be listed in Appendix 16.2.

C-SSRS

The following will be summarized and analyzed separately for the double blind and open label study phases:

- 1. To assess safety:
 - a. **Suicidality:** The number and percentage of subjects reporting any suicidal ideation or behavior throughout the assessment period.
 - b. **Suicidal behavior only:** The number and percentage of subjects reporting any type of suicidal behavior throughout assessment period.
 - c. **Suicidal ideation only:** The number and percentage of subjects reporting any type of suicidal ideation throughout assessment period.

In addition, taking into account baseline data regarding suicidal ideation to determine if suicidal ideation or behavior has worsened:

d. **Emergence of suicidal ideation:** The number and percentage of subjects reporting no suicidal ideation at baseline and any type of ideation during the assessment period.

Effective: 14-Feb-13

Page 21 of 26

- e. Emergence of serious suicidal ideation: The number and percentage of subjects reporting no suicidal ideation at baseline and had serious suicidal ideation (as defined above; score of 4 or 5 on suicidal ideation severity rating) during the assessment period.
- f. **Worsening of suicidal ideation:** The number and percentage of subjects whose most severe suicidal ideation rating is more severe than it was at baseline.
- g. **Emergence of suicidal behavior:** The number and percentage of subjects who had no suicidal behavior at baseline and any type of behavior during the assessment period.

For each of the above endpoints a-g, Fisher's Exact test will be used to test for a difference between the 2 Lofexidine treatment groups and placebo during the double blind phase only.

Physical Examination

The body systems within the physical examination data at screening, baseline (day 1), day 7 and end of the study will be summarized by treatment (Normal; Abnormal NCS, Abnormal CS). The changes from baseline to end of the study in bodyweight will also be tabulated.

Concomitant medications

Concomitant medication verbatim terms (as recorded on the CRFs) after the initial dose of study drug will be mapped to Anatomical Therapeutic Chemical (ATC) Level 2 and Drug Reference Names using the World Health Organization (WHO) dictionary (Version 3.13 Enhanced) and tabulated by treatment group and overall.

Psychosocial Therapy Sessions

- Whether subject received or participated in Psychosocial Therapy Sessions during the double blind phase (Yes, No). If yes, whether received the following
 - o Group Counselling Session (Yes, No)
 - o Art or Music therapy (Yes, No)
 - 12-Step Program Participation (Yes, No)
 - o Other (Yes, No)

Details of the Day 30 Follow-Up

- Lost to Follow-up
- Whether subject successfully entered one of the following programs:
 - o None
 - o Methadone
 - o Buprenorphine

Effective: 14-Feb-13

Page 22 of 26

- o Naltrexone
- o Other
- Whether subject relapsed to drug use after exiting the study (Yes, No)

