#### **14.3.4 Days 8-14 (Open-Label, Continuation Treatment)**

Subjects who successfully meet the definition for “completer” based on Days 1-7 (i.e., receives at least one dose of study medication on Day 7 and completes the 3.5-hour post-dose SOWS-Gossop assessment on Day 7) and if clinically indicated (as determined by the Site Investigator) may continue to receive lofexidine to control symptoms for up to an additional 7 days during Days 8-14. Subjects may be treated as inpatients or outpatients, depending on the wishes of the investigator and the subject, using open-label, variable dose lofexidine (as determined by the Site Investigator, but not to exceed 3.2 mg/day). The rationale for the decision to continue treatment or not and the Site Investigator’s decision to continue treatment through either an inpatient or outpatient setting must be documented in the subject’s source document and eCRF. Lofexidine treatment will terminate and the subject will be discontinued from the study when the Site Investigator judges that the acute phase of opioid withdrawal is essentially complete and the subject no longer needs treatment for abstinence. In any event, no subject will continue to receive lofexidine treatment for more than 14 days total from the onset of abstinence. If being treated as an outpatient, the subject must return to the clinic daily for assessment (see a complete list of assessments in [Table 1](#) of [Section 15](#)).

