## 14.5 Study Discontinuation

### 14.5.1 Subject Discontinuation

A subject can withdraw his/her consent for participation in the study at any time without prejudice. The Site Investigator may discontinue a subject if s/he deems it clinically appropriate for any reason. Additionally, the Site Investigator must discontinue a subject for any of the following reasons:

1. Cardiovascular events (see [Section 14.5.2](#)).
2. Serious medical problem thought to be related or unrelated to the study medications.
3. Intercurrent illness or medical complications that, in the opinion of the site investigator, preclude safe administration of study medications.
4. Evidence of illicit drug use while participating in the study during Days 1-7.
5. Alcohol or other sedative/hypnotic withdrawal signs and symptoms developing following enrollment into the study.
6. Requiring therapy with an exclusionary drug.
7. Lack of compliance with protocol and/or unit procedures.
8. During Days 1-7, missing more than 2 doses of study medication in a single 24-hour period or missing more than 6 doses of study medication prior to meeting “completer” criteria (i.e., receives at least one dose of study medication on Day 7 and completes the 3.5-hour post-dose SOWS-Gossop assessment on Day 7).

At any time after a subject meets “completer” criteria, they may be discontinued by the Investigator if s/he feels that the subject has achieved the treatment goal of acute detoxification/ transition. This judgment by the Site Investigator will be made and recorded daily in the subject’s source document and on the eCRF on Days 7 (after end of double-blind dosing but before initiating open label dosing) through 14.

Subjects who are removed from study treatment because of adverse events (AEs) or serious adverse (SAEs) will be followed until they are medically stabilized to the satisfaction of the attending physician (see [Sections 15.5.1](#), [16.7](#), and [16.8](#)). Appropriate safety evaluations will continue to be collected until the subject is discharged from the treatment center or the maximum 14-day treatment period has expired. This stabilization can include medically supervised opioid withdrawal (involving behavioral therapy, rescue opioid medications, and/or non-opioid pharmacotherapy) or referral to an appropriate methadone or buprenorphine therapy program.

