- (j) Vital signs (resting [sitting/recumbent] and standing blood pressure, and pulse) will be measured at least once daily before dosing and 3.5 hours after dosing on Days 8-13 and once before any dose on Day 14. Oral temperature and respiration are not required measurements Days 8-14. Note that if subjects are being treated on an outpatient basis and cannot stay in the clinic for measurement of the 3.5-hour post-dose vital signs required on Days 8-13, they will be given a portable digital blood pressure machine for measurement of their vital signs at this required time point. They will also be provided a diary to record the measurements.
- (k) Baseline 12-lead electrocardiograms (ECGs) will be done on one day during the screening period, time-matched to the post randomization ECG schedule (i.e., pre-1 PM [before 1 PM dose], 4 PM [3 hours post-dose], and 5 PM [4 hours post-dose]).
  - (l) 12-lead ECGs will be done before the first daily dose, pre-1 PM dose, at 4 PM, and at 5 PM on Days 1 and 7; and before the first daily dose only on Days 2 and 4.
  - (m) 12-lead ECGs will be done before the first daily dose and 3.5 hours after first daily dose on Day 8; on Day 14, the ECGs will be done before a dose on that day.
  - (n) A finger prick blood sample will be collected concurrently with each scheduled ECG during Days 1-7.
  - (o) Clinical lab testing will be done as clinically warranted throughout the study and at the end of double-blind dosing and before initiating open-label dosing.
  - (p) A complete physical examination will be performed during screening and the physical exam form will be updated at Baseline. A complete physical examination will be performed on Day 1 (3-4 hours after randomization) and at the end of double-blind dosing and before initiating open-label dosing. During Days 8-14, a complete physical exam will be performed as clinically warranted and at discontinuation from the study.
  - (q) Urine drug screen will be done at least every other day to monitor for contraband (inpatient setting) or illicit (outpatient setting) drug use.
  - (r) A finger prick blood sample will be collected at 9 PM and 10 PM (3 and 4 hours, respectively, after the 6 PM dose).

209229

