Only days when the patient was taking active treatment will be considered. Days after active administration will be disregarded.

For the calculation of the daily number of medications taken, the number of distinct coded drug names via the WHO dictionary will be used rather than verbatim terms.

Justification

To make the definitions within this analysis clearer.

Change 14

Section 6.13 Safety analysis

Add the text in bold

All subjects who receive at least dose one of study medication will be included in the analysis of safety.

Safety measures will be summarized for the following subject cohorts for the open label phase:

- \neq All treated subjects;
- ≠ Treated subjects without urinary evidence of illicit drug use (i.e. any positive result in the urine drug screen during the open-label phase, including all categories); and
- ≠ Treated subjects with urinary evidence of illicit drug use (may be further subdivided by type of illicit drug used).

Safety measures will only be summarized for all treated subjects for the double blind phase.

Extent of exposure

Extent of exposure will be described by whether the subject took the trial medication and the number of days exposure to double-blind study medication (last date of double-blind medication minus first date of double-blind medication + 1). Average daily dose of double-blind study

Effective: 24-Dec-2014

Page 13 of 29

medication will also be calculated **by number of doses/exposure (days)**. Exposure to open-label medication will also be calculated as last date of open-label medication – first date of open-label medication + 1. No allowance will be made for breaks in therapy in the exposure calculations. Average daily dose of open-label study medication will also be calculated. If the date of last dosing is completely missing for the trial medication then the date of last dosing will be taken for analysis purposes as the date the medication was last dispensed. As there are no open-label dosing dates recorded on the eCRF, dates of visits will be used instead. In particular it will be assumed that open-label dosing starts one day after double-blind dosing ceases.

Justification

To make the definitions clearer.

Change 15

Section 6.13 Safety analysis

Vital Signs During the Double-Blind Phase

The following text was amended:

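### The open-label safety tables split by any positive urine screen make no allowance for length of stay, so they can differ for reasons other than drug use.

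*SAP*

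**What the plan says.** SAP 6.13 and Protocol 17.3.2 name three cohorts for open-label safety: all treated subjects, those without urinary evidence of illicit use, and "Treated subjects with urinary evidence of illicit drug use (may be further subdivided by type of illicit drug used"). Addendum 1, Change 14 (SAP 6.13) supplies the definition: "any positive result in the urine drug screen during the open-label phase, including all categories". It is attached to the 'without' bullet, where read literally it is backwards. It makes sense only as a definition of urinary evidence, and I read it so.

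Other provisions that bear on the point:

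- **Screening.** Protocol Table 1, footnote (q): "Urine drug screen will be done at least every other day". Protocol 15.3.3 and Table 1 add a urine screen at study exit.
- **Stay.** Protocol 14.3.4 allows lofexidine "for up to an additional 7 days during Days 8-14", ending on the investigator's judgment that acute withdrawal is essentially over.
- **After a positive.** Protocol 14.5.1 makes stopping mandatory for "Evidence of illicit drug use while participating in the study during Days 1-7". No automatic stop for a positive screen applies in Days 8-14.
- **AE tables.** SAP 6.13: "All AEs reported whilst receiving Lofexidine therapy will be listed and tabulated by treatment, severity, relationship to study medication", among other factors. Nothing there sets a landmark, divides events at the first positive screen or uses person-time.

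**The concern.** Cohort membership depends on the whole Days 8-14 screen history but is applied back to the first open-label day. This has two consequences. The number of screens, and so the chance of at least one positive, rises with days on study, as does the chance of at least one AE. And an AE on open-label day 2 in a subject first positive on day 5 is counted in the 'with' table.

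At stake is how the two tables read side by side. A difference could be taken as an effect of illicit use on lofexidine safety, or its absence as reassurance, when either could come from who stayed how long. The all-treated summary and the double-blind analyses are untouched.

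**Working it through.** The plan gives no figure to reproduce here, so the check asks what the tables would show if drug use had no effect on AEs.

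**Inputs from the documents:** stay of up to 7 days; screens at least every other day plus one at exit; no mandatory stop for a positive in Days 8-14.

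**Assumptions (the documents give none of these):** stay L uniform on 1-7 days; screens on open-label days 1, 3, 5 and 7 up to exit, plus one on the exit day if not already due; positivity p = 20% per screen; AE risk h = 10% per day, unrelated to screen results; only events during the stay counted.

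**Case A: screens independent, nobody leaves because of a positive.** With k screens, the chance of entering the 'with' cohort is q = 1 - 0.8^k; the chance of an AE is r = 1 - 0.9^L.

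| L | k | q | r | q × r |
|---|---|---|---|---|
| 1 | 1 | 0.200 | 0.100 | 0.020 |
| 2 | 2 | 0.360 | 0.190 | 0.068 |
| 3 | 2 | 0.360 | 0.271 | 0.098 |
| 4 | 3 | 0.488 | 0.344 | 0.168 |
| 5 | 3 | 0.488 | 0.410 | 0.200 |
| 6 | 4 | 0.590 | 0.469 | 0.277 |
| 7 | 4 | 0.590 | 0.522 | 0.308 |
| Sum | | 3.077 | 2.305 | 1.138 |

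- With: 1.138 / 3.077 = 37.0%.
- Without: (2.305 - 1.138) / (7 - 3.077) = 29.7%.
- Gap: +7.3 points, ratio 1.24. Mean stay is 4.57 versus 3.55 days, and 34% of 'with' days precede the first positive.

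Over p of 5% to 30% and h of 5% to 20%, still with nobody leaving, the ratio runs from 1.15 to 1.34, and 30% to 40% of 'with' days precede the first positive.

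**Case B: positivity is a fixed trait shown at the first screen.** Extra screens add nobody, so both cohorts have the same stays: 2.305 / 7 = 32.9% each. Gap zero.

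**Case C: everyone leaves at the first positive.** The 'with' stay is then the day of that screen. Summed over the seven values of L, with weight 0.2 × 0.8^(i-1) for a first positive at screen i:

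- Screen 1 (day 1): weight 7 × 0.2 = 1.400; AE sum 1.400 × 0.100 = 0.140.
- Screen 2 (day 2 once, day 3 five times): weight 6 × 0.16 = 0.960; AE sum 0.16 × (0.190 + 5 × 0.271) = 0.247.
- Screen 3 (day 4 once, day 5 three times): weight 4 × 0.128 = 0.512; AE sum 0.128 × (0.344 + 3 × 0.410) = 0.201.
- Screen 4 (day 6 once, day 7 once): weight 2 × 0.1024 = 0.205; AE sum 0.1024 × (0.469 + 0.522) = 0.101.

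With: 0.690 / 3.077 = 22.4%. Without: 29.7%, as in case A. Gap: -7.3 points.

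**Case D: half leave at the first positive.** With: (37.0 + 22.4) / 2 = 29.7%, against 29.7%. Gap zero.

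**Person-days.** If the daily risk is constant and AEs do not alter stay, expected events equal h times days in every cohort and every case, so the null rate ratio is 1.00.

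**The case against.** A reader might infer that the 'with' cohort must show more events even when drug use is harmless, making the 'without' cohort look safer than it is. The documents do not support that. It needs screens that vary from day to day within a subject, and subjects who stay on after a positive. Neither is given. Protocol 14.5.1 drops the automatic stop after Day 7 but still lets the investigator discontinue anyone on clinical grounds and requires it for non-compliance. The amendment rationale for that section has positive subjects stay only while the investigator considers it safe. Cases B to D show what this does: the gap can vanish or reverse.

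A reader might also infer that the plan attributes these events to illicit use. It does not. The cohorts are descriptive, no test between them is planned, no purpose is stated, and a subject-level 'without' cohort is a legitimate description of people who never screened positive. SAP 6.13 also derives days of open-label exposure and lists AE onset times, though it does not promise exposure by cohort.

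Dividing time at the first positive has its own flaw: a positive reflects use before the screen, so some days of use fall on the 'before' side.

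All of this stands, and it limits the point to presentation. It does not remove it: the tables still make no allowance for stay, whichever way the imbalance runs.

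**Conclusion.** The point holds as a minor one. The cohorts rest on the full open-label screen history, AEs are reported without allowance for differing stay, and events before the first positive fall in the 'with' table. The two tables can therefore differ with no effect of drug use.

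Under the assumptions above, the null gap in subjects with an AE runs from about +7 points (nobody leaves after a positive) through zero (fixed-trait positivity, or half leaving) to about -7 points (all leaving). The documents give no basis for choosing among these, so no single size or sign should be quoted. No efficacy result and no all-treated safety summary is affected.

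**What to change.** In SAP 6.13, keep the subject-level cohorts and add three things for open-label AEs:

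1. Person-days and events per person-day in each cohort, counting events with onset on open-label study days. SAP 6.13 treats onsets up to 30 days after the last dose as treatment emergent; events and days must cover the same window.
2. Within the 'with' cohort, events and days shown separately before and from the first positive screen.
3. That display by study day. If AE risk falls over Days 8-14, the later days would otherwise look safer for that reason alone.

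Move the Change 14 definition to the 'with' bullet in the same edit. Its inclusion of all categories should also be reconciled with Protocol 14.6, which permits a short-acting benzodiazepine in Days 8-14 while Protocol 15.5.4.3 has benzodiazepines on the panel.

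The cost is SAP wording and table programming; no new assessment is needed. The downsides should be stated with the tables. A positive screen reflects earlier use, so its date is an imperfect marker of onset. Change 14 says open-label dosing dates were not recorded and visit dates stand in, so person-days are approximate. The split suits AEs, not laboratory summaries based on the last open-label assessment.
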